### 10.2. STUDY POPULATIONS

Different population of patients may be defined for the analysis:

- Intent To Treat (ITT) population: all included patients.
- Per-Protocol (PP) population: all eligible patients (patients with no major violations of the inclusion/exclusion criteria) and evaluable patients (included treated patients with evaluation at 48 weeks or without evaluation at 48 weeks if progressive or dead patient).
- Safety population: all treated patients who received at least one dose of treatment.

### 10.3. STATISTICAL METHODS

A statistical analysis plan (PAS) will be written before the closed database. All statistical analyses will be performed on ITT population, on PP population for efficacy analysis and on Safety population for safety analysis. Populations are defined in section 10.2.

Descriptive analyses will be performed using median and range for continuous parameters, frequency and percentage for categorical variables.

Incidence rate of DLT and Incidence rates of adverse events and serious adverse events will be carried using frequencies and percentages at each dose level for phase 1.

The primary phase II endpoints 48 weeks disease control rates, will be described using percentage and its associated 95% confidence interval.

The median follow-up will be calculated using the reverse Kaplan-Meier method with its confidence interval of 95%.

All event free survival (PFS, OS) will be estimated using the Kaplan-Meier method, and then described using medians and rates with their associated 95% confidence interval.

Statistical analyses will be performed with STATA software (Stata Corporation, College Station, TX, USA).

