## 9.4. ASSESSMENT CRITERIA

Phase I: Identify the maximum-tolerated dose (MTD) of Folfirinox combination with regorafenib in Patients with metastatic colorectal cancer.

Phase II:

Non-progression rate (OR+SD): The tumor response will be assessed by the investigator using RECIST guidelines v1.1 (2009). The non-progression rate will be presented as a percentage with a 95% confidence interval.

Objective response (OR): The tumor response will be assessed by the investigator using RECIST v1.1 criteria, from the first course of chemotherapy, until disease progression. Patients with suggestive symptoms of disease progression should be evaluated at the time of onset of symptoms. An objective response is defined as a complete (CR) or a partial (PR) response.

The best objective response rate will be reviewed at the end of treatment and presented as a percentage with a confidence interval of 95%.

Survival:

Progression-free survival (PFS): Survival Delays will be calculated in months from the date of inclusion to the date of the considered event: First documented disease progression or death from any cause.

Living patients without disease progression will be censored at the last known date.

Rates and median PFS will be estimated using Kaplan-Meier method and presented with its 95% confidence interval.

Overall survival (OS): The overall survival time will be calculated in months from the date of inclusion to the date of death from any cause. Living patients will be censored at the last known date.

Rates and median overall survival will be estimated using the Kaplan-Meier product limit method and presented with its 95% confidence interval.

The median follow-up will be calculated using the "reverse Kaplan-Meier method".

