#### Phase II

With a one-stage Fleming design,  $\alpha = 5\%$ ,  $\beta = 20\%$ ,  $p_0$  (the probability of inefficiency maximum) = 35% and  $p_1$  (the probability of minimum efficiency) = 50%, it would be necessary to include 65 evaluable patients (69 patients/ 5% non-evaluable patients).

The association can be considered sufficiently effective (reject null hypothesis) if there are at least 29 success (48 weeks disease control rate) out of 65 evaluable patients, the success rate is significantly greater than 35%.

The association can be considered insufficiently effective (reject alternative hypothesis) if there are 28 or less success out of 65 evaluable patients, the success rate is significantly lower than 50%.

In total, a maximum of 87 (=18 patients for phase I + 69 patients for phase II including 6 patients treated at the RP2D during the phase I) patients will be included.

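### The phase II alpha is not labelled one-sided, and the 29/65 efficacy rule is never reconciled with the descriptive 95% interval for the primary endpoint

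*Combined protocol and SAP*

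**What the plan says.** Section 10.1 (Phase II) and the statistical part of the synopsis set out the design. It opens "With a one-stage Fleming design", with alpha 5%, beta 20%, p0 ("the probability of inefficiency maximum) = 35"%) and p1 ("the probability of minimum efficiency) = 50"%). The resulting size is given as "it would be necessary to include 65 evaluable patients (69 patients/ 5% non-evaluable patients"). Neither place says whether alpha is one- or two-sided.

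The same text fixes the decision. The null is rejected "if there are at least 29 success (48 weeks disease control rate) out of 65 evaluable patients", and at that count the plan says "the success rate is significantly greater than 35"%. With 28 or fewer successes the combination is judged insufficiently effective.

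Two other sections deal with reporting. Section 10.3 says: "The primary phase II endpoints 48 weeks disease control rates, will be described using percentage and its associated 95% confidence interval". Section 9.4 says: "The non-progression rate will be presented as a percentage with a 95% confidence interval". Neither names an interval method, compares the interval with 35%, or refers to the 29/65 rule. Section 10.3 also says that a separate statistical analysis plan will be written before the database is closed.

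**The concern.** A one-sided 5% test against 35% corresponds to the lower limit of a two-sided 90% interval. A conventional two-sided 95% interval places 2.5% on each side. If the design uses the first and the report shows the second, there are counts at which the protocol declares the rate significantly above 35% while the interval printed beside it still includes 35%.

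The trial is single-arm and open-label, and its main conclusion rests on this one comparison. At a borderline count, readers of the report could not tell from the protocol which statement to rely on or what error level the claim carries. It also matters whether the stated cut-off meets the stated alpha under any reading of sidedness, because that determines whether relabelling alone would be enough.

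**Working it through.** **Inputs.** From section 10.1 and the synopsis: p0 = 0.35, p1 = 0.50, alpha = 0.05, beta = 0.20, 65 evaluable, 5% non-evaluable, cut-off 29. From sections 10.3 and 9.4: a 95% interval, taken here as two-sided because that is the convention; the documents do not say. All counts below assume exactly 65 evaluable patients.

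**Step 1: reproduce the size.** Single-stage normal approximation:

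n = [(z_alpha × √(p0(1 − p0)) + z_beta × √(p1(1 − p1))) / (p1 − p0)]²

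with √(0.35 × 0.65) = 0.4770, √(0.50 × 0.50) = 0.5 and z_beta = 0.8416.

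- One-sided 5% (z = 1.645): (0.7845 + 0.4208)/0.15 = 8.036, squared = 64.6, rounded up to **65**. Then 65/0.95 = 68.4, rounded up to **69**. Both plan figures are reproduced.
- Two-sided 5% (z = 1.960): (0.9348 + 0.4208)/0.15 = 9.038, squared = 81.7, rounded up to 82. This is not the plan's figure.

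So the design rests on a one-sided 5% alpha that is not written down.

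**Step 2: check the cut-off.** On the normal approximation the boundary is 65 × 0.35 + 1.645 × √(65 × 0.35 × 0.65) = 22.75 + 1.645 × 3.845 = 29.08, so 29 falls just short. The score statistic at 29/65 is (0.4462 − 0.35)/√(0.35 × 0.65/65) = 1.625, below 1.645. At 30/65 it is 1.885.

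Exact binomial properties at n = 65:

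| Rule | Type I error, P(X ≥ r) at 35% | Power, P(X ≥ r) at 50% |
|---|---|---|
| r = 29 (plan) | 6.9% | 83.9% |
| r = 30 | 4.1% | 77.1% |

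The stated rule exceeds one-sided 5% both exactly and by the normal approximation. The smallest cut-off that keeps 5% is 30.

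**Step 3: compare with the intervals (exact, Clopper-Pearson).**

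| Successes | Rate | Exact one-sided p | 90% interval | 95% interval |
|---|---|---|---|---|
| 29/65 | 44.6% | 0.069 | 34.1% to 55.5% | 32.3% to 57.5% |
| 30/65 | 46.2% | 0.041 | 35.5% to 57.1% | 33.7% to 59.0% |

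The method does not rescue the 95% interval. The lower limits are 33.2% (Wilson) and 32.5% (Wald) at 29, and 34.6% and 34.0% at 30. All are below 35%.

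**Step 4: separate the two causes.**

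- At 30/65 the one-sided test and the 90% interval agree that the rate exceeds 35%; only the 95% interval does not. This is a pure conflict of sidedness.
- At 29/65 the one-sided test and the 90% interval also fail to exclude 35%. The disagreement comes from the cut-off and would remain after relabelling alpha.

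**Step 5: how likely is the pure conflict?** P(X = 30) with n = 65 is 8.2% at a true rate of 50%, 9.7% at 45% and 1.8% at 35%.

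**The case against.** The strongest reply is that nothing here contradicts anything else. The plan has one decision rule, the count in section 10.1. The interval in section 10.3 is there to describe the rate, and the same 95% level is used for response, progression-free survival, overall survival and follow-up, so it is a reporting convention. A directional design with a descriptive 95% interval beside it is ordinary practice. The direction can be inferred from the wording of the efficacy rule and from the size, and the interval method can be left to the later analysis plan.

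Much of this stands, and it rules out three stronger readings that a reader might infer.

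- *That the 95% interval is the only planned analysis of the primary endpoint.* It is not: section 10.1 and the synopsis pre-specify the 29/28 rule.
- *That the design really needs 31 successes and has only 69% power.* Those figures describe using the 95% interval as the test, which no section proposes.
- *That 29 and 30 are both sidedness conflicts, with a joint probability of 15.0% at a true rate of 50%.* Only 30 is. The problem at 29 is the cut-off.

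What the reply does not answer is that sidedness is missing, that the plan calls 29/65 significant when it is not at one-sided 5%, and that no text links rule and interval. Leaving this to the analysis plan is weak protection, because that plan is required only before database closure and the trial is open-label and uncontrolled, so outcomes could be known by then.

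**Conclusion.** The point holds as a failure to state sidedness and to reconcile rule, alpha and interval; it does not make the analysis invalid. The size of 65 rests on an unstated one-sided 5% alpha. At 30/65 the design's test is met while the conventional 95% interval contains 35%, with probability 8.2% to 9.7% for true rates of 50% to 45%. At 29/65 the plan's claim of significance is made at an exact level of 6.9% against the stated 5%.

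This rests on exactly 65 evaluable patients, on reading the 95% interval as two-sided, and, for the exact figures, on Clopper-Pearson limits and binomial tails. The finding that 35% lies inside the 95% interval at both counts is the same with Wilson and Wald limits.

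**What to change.** - **Section 10.1 and synopsis:** write that alpha is one-sided 5%. State that efficacy is decided by the exact one-sided binomial test against 35%, equivalently by whether the lower limit of the exact 90% interval exceeds 35%. Change the cut-off to at least 30 of 65, with 29 or fewer as failure. Restate the properties as exact type I error 4.1% and power 77.1%, in place of 5% and 80%.
- **Sections 10.3 and 9.4:** report the exact 90% interval and the exact one-sided p-value for the primary endpoint. If a 95% interval is also shown, name its method and label it descriptive, with no part in the decision.

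**Cost.** This is a change to the protocol text and the analysis plan, with no added patients or data. It is more than relabelling: the cut-off moves up by one success and power falls from 83.9% under the present rule to 77.1%, slightly below the stated 80%. That loss should be disclosed. If 80% must be kept, the smallest exact one-sided 5% design is 68 evaluable patients with at least 31 successes (type I error 4.6%, power 80.2%). With 5% non-evaluable that is 68/0.95 = 71.6, so 72 patients, three more than the planned 69.

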## 11. Vigilance and safety control

### 11.1. ADVERSE EVENTS

#### 11.1.1. DEFINITION

An Adverse Event (AE) is defined as “Any untoward medical occurrence in a patient or clinical investigation subject administered an investigational product and which does not necessarily have a causal relationship with this treatment”. An AE can therefore be any unfavorable and unintended sign (for example: an abnormal laboratory finding), symptom, disease, or worsening of a pre-existing medical condition temporally associated with the use of an investigational product, whether or not considered related to the investigational product.

Only abnormal laboratory findings which are clinically significant should be considered an AE. Abnormal laboratory findings are clinically significant if an active medical intervention is indicated, such as a dose modification of the investigational product ; an interruption of the investigational product; the withdrawal of the investigational product; the introduction of a (symptomatic) treatment; the performance of additional diagnostic procedures; the increase in monitoring frequency.

An AE related to the investigational product is also called an adverse reaction.

#### 11.1.2. COLLECTION AND REPORTING

Every AE occurring during the clinical trial should be recorded on the corresponding page of the Case Report Form. Every AE should be documented, monitored and followed until the AE is recovered or until the safety follow-up visit is performed at 30 days after the withdrawal of the investigational product.

Clinically significant abnormal laboratory findings should be monitored regularly by specific analysis until their values return within the normal reference ranges, to the baseline value or until an adequate explication of the out of range value has been found. Per the applicable regulations, AEs are collected from the moment of signature of the informed consent form until up to 30 days after the withdrawal of the investigational product.

For every AE, the following parameters will be documented by the investigator:

- A clear description of the event using the adequate medical terms;
- The seriousness of the event;
- The severity or grade of the event (severity criteria are described in the next paragraph);
- The onset and end dates of the event;
- The actions taken and the necessity to introduce a corrective treatment or not;
- Whether the AE caused or not the withdrawal of the subject from the study;
- The outcome of the event. In case of a non-fatal outcome, the AE should be documented until recovered, until the return to baseline conditions of the event or until stabilization of the event's sequelae (the nature of the sequelae should be documented) ;
- The causality between the event and the investigational product ;

- The eventual causality between the event and the study procedures (time laps without treatment, complementary assessments required by the protocol, etc....), the study indication, a concomitant treatment, a concomitant pathology or another factor.

#### 11.1.3. SEVERITY CRITERIA

The severity criteria should not be mistaken with the seriousness criteria which determine the conditions of notification. The severity or grade of adverse events is evaluated by the investigator following the NCI-CTCAE classification version 5.0 (appendix 9).

The CTCAE displays Grades 1 through 5 with unique clinical descriptions of severity for each AE based on this general guideline:

- **Grade 1** = Mild; asymptomatic or mild symptoms; clinical or diagnostic observations only; intervention not indicated.
- **Grade 2** = Moderate; minimal, local or non-invasive intervention indicated; limiting age-appropriate instrumental ADL\*.
- **Grade 3** = Severe or medically significant but not immediately life-threatening; hospitalization or prolongation of hospitalization indicated; disabling; limiting self-care ADL\*\*.
- **Grade 4** = Life-threatening consequences; urgent intervention indicated.
- **Grade 5** = Death related to AE.

\*Instrumental ADL refer to preparing meals, shopping for groceries or clothes, using the telephone, managing money, etc.

\*\*Self-care ADL refer to bathing, dressing and undressing, feeding self, using the toilet, taking medications, and not bedridden.

## 11.2. SERIOUS ADVERSE EVENTS AND NEW EVENT

### 11.2.1. DEFINITION

A **Serious Adverse Event (SAE)** is an adverse event which:

- results in death
- is life-threatening
- requires in-patient hospitalization or prolongation of existing hospitalization,
- results in persistent or significant disability or incapacity

- Is a congenital anomaly or birth defect
- Is medically relevant

Life-threatening in this context refers to an event in which the patient was at risk of death at the time of the event; it does not refer to a reaction that hypothetically might have caused death if more severe.

A hospitalization scheduled by the protocol (biopsy, chemotherapy...) is not considered a SAE. A hospitalization or prolongation of hospitalization for technical, practical, or social reasons, in absence of an AE is not considered a SAE. A hospitalization planned prior to patient enrollment is not considered a SAE, provided that his occurrence/outcome is clearly not aggravated by the investigational product.

The terms “disability” and “incapacity” match with all physical/psychological temporary or permanent handicaps, clinically significant with consequences for the physical or mental functioning and/or the quality of life of the patient.

Medical and scientific judgment should be exercised in deciding whether other situations should be considered serious events, such as important medical events that might not be immediately life-threatening or result in death or hospitalization but might jeopardize the patient or might require intervention to prevent one of the other outcomes listed above. Such events are considered serious with seriousness criterion “medically relevant”. Examples of such events are allergic bronchospasm, torsade de pointes (appendix 8) or convulsions.

Other examples of serious adverse events with seriousness criterion “medically relevant” are second primary malignancies and any suspected transmission via a medicinal product of an infectious agent.

For every SAE the investigator and the sponsor evaluate separately the possible causal relationship to the investigational product. These evaluations might be different one from the other (for example: in the investigator’s opinion the SAE is not related to the investigational product and in the sponsor’s opinion the SAE is related to the investigational product).

**A New event** (article R1123-46 du CSP) is:

Any new data that may lead to a re-assessment of the benefit/risk ratio of the clinical trial or the investigational medicinal product (IMP), to modifications of the use of the IMP or the conduct of the trial or modifications of documents regarding the trial or to the suspension or termination of the clinical trial or to modify the protocol of the trial concerned or other similar trials.

For a first in man study conducted in healthy volunteers: any serious adverse reaction (SAR) of the IMP is considered to be a new event

#### **11.2.2. URGENT SAFETY MEASURE (USM) (ARTICLES L.1123-10 ET R. 1123-62 CSP)**

When a suspicion of an Unexpected Serious Adverse Reaction (SUSAR) or a New Event is likely to affect the safety of the subjects, or the IMP is likely to affect the safety of the participant who lend themselves to it with immediate endangerment, the sponsor and investigator put in place Urgent Safety Measure (USM) to protect the subjects against this immediate hazard, the sponsor and the investigator concerned take the necessary appropriate Urgent Safety Measures (USM).

#### **11.2.3. SUSPECTED UNEXPECTED SERIOUS ADVERSE REACTION**

A SAE is qualified as a Suspected Unexpected Serious Adverse Reaction (SUSAR) when a causal relationship between the investigational product and the SAE is suspected and when the nature, the severity, the frequency or the evolution of the reaction does not match with the information available in the reference document. The sponsor evaluates the unexpectedness of the SAE by consulting the SmPC of Oxaliplatin, 5 FU, Irinotecan and the investigator's brochure in force for Regorafenib.

#### **11.2.4. PREGNANCY**

For female patients treated with the investigational product, the treatment with this product should be discontinued immediately at the occurrence or suspicion of occurrence of pregnancy and the patient should be withdrawn from the study (after confirmation of the pregnancy by a urine or blood test).

The pregnancy should be followed up to determine outcome, including spontaneous or voluntary termination, details of the birth, and the presence or absence of any birth defects, congenital abnormalities, or maternal and/or newborn complications.

In accordance with the recommendations for fertility preservation, the investigator may propose to the patient a protocol of conservation of ovocytes for women and of sperm cells for men.

#### **11.2.5. SAE, NEW EVENT, URGENT SAFETY MEASURE, PREGNANCY NOTIFICATION PROCEDURE**

##### **11.2.5.1. SAE NOTIFICATION PROCEDURE**

Every SAE, expected or unexpected, occurring during the study period (from the moment of signature of the informed consent form until up to 30 days after the withdrawal of the investigational product) should be notified to the sponsor without any delay using the "Serious Adverse Event Notification Form" (appendix 10). This form should be completed following the completion instructions (appendix 10) and sent by email to the Clinical Research Pharmacovigilance Unit of ICM.

#### **Clinical Research Vigilance Unit**

**ICM – Institut régional de Cancérologie de Montpellier**  
**[name]**  
**[contact] – [contact]**  
**E-Mail: [[contact]](mailto:[contact])**

Every SAE occurring beyond the 30 days period after the withdrawal of the investigational product, judged by the investigator to be related to the investigational product, should also be notified to the sponsor in the same conditions as every other SAE.

The "Serious Adverse Event Notification Form" should be completed in English and only one diagnosis or one symptom (except for linked symptoms) should be reported to enable MedDRA coding. If several symptoms are documented in the source documents, only the main symptom will be reported as verbatim on the notification form.

After the initial notification, a follow-up report should be completed and faxed every time complementary information on the SAE becomes available. Finally, when the case is closed, a final report with the complete information should be completed and sent by email to the Clinical Research Pharmacovigilance Unit :

E-Mail: [[contact]](mailto:[contact])

Complementary information or clarification could be requested by the sponsor using Data Clarification Forms (DCFs). The sponsor could also ask the site to send the anonymized medical records or laboratory findings corresponding to the SAE. In case of a SUSAR a narrative of the case in English is to be provided by the investigator.

#### 11.2.5.2. NEW EVENT / URGENT SAFETY MEASURE (USM)/ NOTIFICATION PROCEDURE

Any New Event and/or Urgent Safety Measure occurring during the study period should be notified to the sponsor without any delay, to Clinical Research Pharmacovigilance Unit:

E-Mail: [[contact]](mailto:[contact])

